4.5 WHAT ARE THE MEASURED OUTCOMES FOR THE PILOT STUDY?

The primary feasibility outcome for the pilot study is the number of participants recruited per centre per month. We will obtain baseline details of the patient's type, location and treatment of cancer, and medications. Secondary feasibility outcomes of the pilot study will include, consent rates, loss to follow up, adherence to therapy defining 80% or greater medication taken as having good adherence to study drug, proportion of screened patients who meet eligibility criteria. We will document reasons for non-consent in order to assist recruitment for the larger multicentre trial.

For the full multicentre trial the outcomes would be as follows: primary outcome of symptomatic, radiographically confirmed VTE. Secondary outcomes include major and CRNMB, CVC life span, premature CVC removal, CVC lumen occlusion, CVC associated infection and death.

4.6 SCREENING

Participants will be screened within 72 hours of CVC insertion.

4.7 RANDOMIZATION

Consenting subjects will be randomized at 1:1 ratio to treatment or non-treatment arms at study enrollment with treatment allocation determined by central web-based randomization. Randomization will be stratified by gender and the type of central venous catheter (Peripherally Inserted Central Catheter or Hickman/Port-a-Cath/Central line).

Participants will be randomized once the participant has consented and all eligibility criteria have been confirmed.

Randomization will be conducted using a customized web-based program developed for this study. The randomization process will be initiated by the local study coordinator who will access

the web-based system and enter the patient's unique identifier and confirmation of eligibility and informed consent. Specific patient allocation will then be electronically delivered, to the research pharmacy who will prepare and dispense trial medication.

4.8 TREATMENT ARMS

Treatment Arm 1: Experimental

Rivaroxaban 10 mg po daily for 90 (+/-3) days. After the Day 90 follow up, the study treatment will be discontinued, and subsequent treatment will be at the discretion of the attending physician.

Treatment Arm 2: Standard of care

No rivaroxaban prophylaxis. Management will be at the discretion of the attending physician.

4.9 PROHIBITED MEDICATIONS DURING THE STUDY

Systemic treatment with strong CYP 3A4 and P-glycoprotein inhibitors (such as ketoconazole, itraconazole, posaconazole, or ritonavir) is a contra-indication to treatment with rivaroxaban and is therefore an exclusion criterion for study entry.

If a participant in the rivaroxaban arm requires initiation of treatment with strong CYP 3A4 and P-glycoprotein inhibitor while on study treatment the participant will be withdrawn from study treatment. The participant may then be switched to an alternative anticoagulant treatment at the discretion of the attending physician.

4.10 PRODUCT LABELLING

Rivaroxaban will be purchased through the research pharmacy and relabeled for this trial according to the template below. Each participant in the treatment arm will be given a 93-day supply of study drug (according to the randomization scheme) at Day 1.

Product information for each of the study medications is listed in Appendix 4.

Rivaroxaban 10 mg Expiration: DD-MMM-YYYY Store at room temperature between +15°C and +25°C Lot # ----- Protocol : TRIM-Line Trial Sponsor: The Ottawa Hospital Research Institute, [name] Investigational drug -- to be used only by a qualified Investigator	Rivaroxaban 10 mg Expiration: JJ-MM-AAAA Conserver à l'air ambiant, entre +15°C et +25°C, Lot # ----- Nom du Protocole: TRIM-Line Trial Commanditaire: Institut de recherche de l'Hôpital d'Ottawa [name] Médicament expérimental -- à être utilisé seulement par un Investigateur qualifié
--	---

4.11 ACCOUNTABILITY AND STORAGE

Study drug will be stored and maintained by the Clinical Trial pharmacy technicians at The Ottawa Hospital. Bulk accountability logs and individual accountability logs will be completed and maintained by the pharmacy technicians. Participants will keep a medication diary. Drug accountability (pill count & review of diary) will be done on Day 90 +/- 3 days when the medication is returned.

Participants will be counseled to keep the study drug in room temperature conditions. The study medication which they take home should not be exposed to extreme temperatures.

4.12 INDIVIDUAL PARTICIPANT COMPLIANCE

Participants will be given a diary and will record the date and time of administration of each dose. If a dose is missed the participant should take it as soon as it is remembered and record the time. The next dose should be taken at the new time. Non-adherent participants may be removed from the study at the discretion of the primary investigator. In order to allow drug accountability by research staff participants will be instructed to return all bottles of study medication.

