Dispense IP (Group 1)	✓		
Concomitant Medications	✓	✓	✓
IP Compliance		✓	✓
Outcome Information (Section 4.5)		✓	✓
Adverse Events		✓	✓

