4.3 TRIAL INTERVENTION

Eligible and consenting patients will receive rivaroxaban 10 mg tablets to be taken once daily, starting within 72 hours of CVC placement. Randomization will occur in a 1:1 ratio via a central web-based randomization system.

The study drug will be continued until the CVC is removed, until one of the study outcomes is achieved, or until the end of the follow-up (90 Days +/- 3 days). Study medication will be held if the platelet count is $50 \times 10^9/L$ or less, the CrCl falls below 30mL/min, the patient experiences bleeding or the patient is required for treatment of cancer to start on a medication or chemotherapy which has a major interaction with rivaroxaban. All patients will be followed for 90 days (+/-3 days), unless they die or withdraw permission for follow up. At the end of the trial, VTE prophylaxis will be left to the discretion of the local investigator.

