4.14 PROPOSED FREQUENCY AND DURATION OF FOLLOW UP

In addition to the initial enrollment visit, patients that are enrolled will receive a telephone follow up at Day-30 +/- 3 days and an in person follow up at Day 90 +/- 3 days.

Post-enrollment follow up visits will include assessment and history for major and minor bleeding, CVC life span, premature CVC removal, CVC lumen occlusion, CVC associated infection and death and assessment of adherence to study drug. Patients will be followed for 90 days +/- 3 days.

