4.15 WITHDRAWAL OF SUBJECTS

A subject has completed the study once all follow-up procedures have been completed. Study drug is discontinued, and appropriate clinical management is initiated in the case of the following outcome events (as defined in section 4.5).

For the subjects who reach a study endpoint, subsequent treatment will be left up to the discretion of the treating physician and documented.

If the subject is prematurely discontinued from participation in the study, the study personnel will make every effort to obtain, and record, information about the reasons for discontinuation and any adverse events and if possible perform all safety assessments.

A subject may voluntarily withdraw participation in this study at any time, including for future data collection. If the subject does not return for a scheduled visit, every effort will be made to contact the subject. In any circumstance, every effort will be made to document the reason for withdrawal and when possible, all safety assessments will be done.

All data will be reported for any subject randomized and not completing the study. Subjects withdrawn as a result of an adverse event thought to be related to the study drug will not be replaced. All safety data collected from all subjects during the study will be analyzed.

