7.2 PROTOCOL VIOLATIONS

Protocol violations refer to more serious incidents involving non-compliance with the protocol that may result in significant effect on the participant's rights, safety, or welfare or data integrity.

Protocol violations could result in the participant being excluded from the eligibility analysis and/or result in the participant being discontinued from the trial. Examples of violations include: non-compliance with inclusion/exclusion criteria and dosing administration.

If non-compliance is identified, the following procedures will be followed:

- All protocol deviations will be recorded in a log
- The site investigator or delegate will notify the coordinating centre in Ottawa as soon as possible after discovering the violation.
- The site investigator or delegate will document: the details and reason for the protocol violation. The documentation will also include an assessment by the site investigator with regards to the impact of the protocol deviation on the participant or trial data. Follow-up procedure and corrective action to prevent future violations will also be documented.
- Violations will be recorded in the study source document and on the protocol violation form

- All violations will be reported to the local research ethics board (according to local policies)
- All violations will be reported and reviewed by the Data and Safety Monitoring Board.

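### Sections 4.12 and 7.2 allow removal from the study, against the 90-day follow-up of all patients in 4.3, and 4.15 does not require the outcomes afterwards

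*Protocol*

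**What the plan says.** **Follow-up.** Section 4.3 states: "All patients will be followed for 90 days (+/-3 days), unless they die or withdraw permission for follow up". Section 4.14 repeats the 90 days and adds no exception.

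**Exits.** Section 4.12 states: "Non-adherent participants may be removed from the study at the discretion of the primary investigator". Section 7.2 Protocol Violations (the DSMB section is also headed 7.2) says that a violation could "result in the participant being discontinued from the trial". Its examples cover both eligibility and dosing, and it names no decision-maker.

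**After an early exit.** Section 4.15 asks staff to record the reasons for discontinuation "and any adverse events and if possible perform all safety assessments". It adds that "every effort will be made to document the reason for withdrawal", and that all data on non-completers will be reported.

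**Wording when only the drug stops.** Section 4.9 says that "the participant will be withdrawn from study treatment".

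**What is scheduled.** The Schedule of Mandatory Events in the synopsis has a row for "IP Compliance" and a row for outcome information that points to 4.5, both ticked at Day 30 and Day 90. The visit list in 4.14 ends with "CVC associated infection and death and assessment of adherence to study drug" and does not itself name VTE.

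**The concern.** A site cannot keep the 4.3 rule and also use the 4.12 or 7.2 exit as written. Non-adherence and protocol violations are not among the two exceptions in 4.3.

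Two results are at stake. First, study drug is given only in the rivaroxaban arm, so removal for not taking it can happen only there. Outcomes not collected after removal would then be missing on one side, for a reason that may be related to outcome. Section 4.2 plans to carry the pilot's clinical data into the full trial if the design does not change materially, and 8.1.4 makes intention to treat primary. An intention-to-treat analysis cannot restore outcomes that nobody collected.

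Second, a removed participant would count in the withdrawal/loss proportion of 8.1.3, and 8.2 says that pilot drop-out will help to size the full trial. Part of that proportion would then reflect investigators' decisions and not participants' willingness to stay.

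**Working it through.** **Text check**

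1. Permitted ends of follow-up in 4.3: death and withdrawn permission.
2. Further exits: non-adherence (4.12, primary investigator decides) and protocol violation (7.2, no decision-maker). Neither falls under step 1, so the sections conflict.
3. Could 4.12 mean the drug only? Section 4.9 refers to study treatment when only the drug stops, while 4.12 refers to the study and 7.2 to the trial. If drug only was intended, sites would still have to guess.
4. Does 4.15 close the gap? It asks for reasons and adverse events, and for safety assessments where possible. Its sentence on reporting all data concerns data already held. It does not require the 4.5 outcomes to Day 90.

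**Size**

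The plan's figure: 860 per arm gives 1720, and 1720 × 1.10 = 1892, as in 8.2. The 860 is taken as given. A two-sided pooled formula with 6.8% and 3.7% gives 812, or 875 with continuity correction; nothing below depends on which was used.

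Assumptions, since the protocol gives no removal rate: 50 per arm (100 patients, 1:1); other losses 10%, that is 5 of 50 in each arm; 0, 2, 6 or 10 rivaroxaban participants removed who would not otherwise be lost; observed loss put directly into the plan's rule 1720 × (1 + loss).

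| Removed of 50 | Combined loss | Rivaroxaban arm | Control arm | Full-trial N |
|---|---|---|---|---|
| 0 | 10/100 = 10% | 5/50 = 10% | 5/50 = 10% | 1892 |
| 2 | 12/100 = 12% | 7/50 = 14% | 10% | 1926 |
| 6 | 16/100 = 16% | 11/50 = 22% | 10% | 1995 |
| 10 | 20/100 = 20% | 15/50 = 30% | 10% | 2064 |

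For scale, the Wilson 95% interval for 10/100 is 5.52% to 17.44%. In the same rule, 1720 × 1.0552 = 1815 and 1720 × 1.1744 = 2020. Only the case of 10 removed lies outside that range.

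Expected events among those removed, at the two risks in 8.2: from 2 × 3.7% = 0.07 to 10 × 6.8% = 0.68. These figures are generous, because they place the whole 90-day risk after removal.

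Share of a full-trial arm if carried forward: 1892/2 = 946; 2/946 = 0.2% and 10/946 = 1.1%.

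**The case against.** The strongest reply is that the protocol already catches much of what removal would lose.

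- **Outcomes.** A reader might infer that VTE is wholly unobserved after removal. The documents do not support that. Section 5.1 defines an adverse event broadly enough to include symptomatic VTE, section 5 runs the reporting period to Day 90 and allows chart review, and 4.15 asks for adverse events after discontinuation. Some VTE, bleeding and deaths may be captured this way. The route has limits: 5.1 leaves out non-serious events possibly related to cancer or its treatment, the definition applies only after a dose of study drug, and 4.15 does not say that collection runs to Day 90 after removal.
- **Adherence.** A reader might infer that adherence data are lost for those removed. However, 4.12 tells participants to return all bottles, without tying this to Day 90, and compliance is also checked at Day 30. A count at removal remains possible.
- **One-sidedness.** A reader might infer that every removal falls on the rivaroxaban arm. This holds for non-adherence to study drug. It does not hold for violations: eligibility errors occur in both arms, and 8.1.3 foresees crossover, so a control participant who receives rivaroxaban could be a dosing violation.
- **Analysis.** A reader might infer that 8.1.3 must split its withdrawal proportion, or that 7.2 overrides intention to treat. The reason for discontinuation is already recorded and a split by reason can be left to the SAP. Section 8.1.4 already makes intention to treat primary.
- **Size.** The removal counts are assumed, and 8.2 says only that pilot data will help with sizing, not that observed loss is inserted mechanically.

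All of this limits the consequences. It does not remove the conflict between 4.3 and the two exits, or supply the missing requirement in 4.15.

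**Conclusion.** The contradiction stands and is worth correcting, but its expected effect in this pilot is small. Section 4.3 cannot be met if 4.12 or 7.2 is used as written, and 4.15 then leaves the 4.5 outcomes to be captured partly and by chance.

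On the stated assumptions, up to 6 of 50 removals move the loss estimate by less than its own sampling error, and only 10 of 50 goes beyond it. Less than one expected event is involved, in at most 1.1% of a full-trial arm. If removal is never used, the effect is zero. The primary outcome, recruitment per centre per month, is untouched in every case.

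A reader might infer that the pilot's feasibility conclusions, or the full trial's result, would be seriously biased. The documents do not support this: they give no removal rate, and they give adverse event reporting as a partial second source. The case for changing the text is that the missing data would be avoidable, would arise mainly in one arm, and could not be recovered at analysis.

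**What to change.** Reconcile 4.3, 4.12, 4.15 and 7.2 Protocol Violations so that ending study drug and ending follow-up are separate events.

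- **4.12:** state that non-adherence does not by itself end follow-up.
- **7.2 Protocol Violations:** state that a violation does not by itself end follow-up.
- **4.15:** state that the Day 30 and Day 90 outcome information on 4.5, already listed in the Schedule of Mandatory Events, continues to be collected after discontinuation, with only the two exceptions in 4.3.

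Decisions about study drug stay as they are, and neither 8.1.3 nor 8.1.4 needs a change. The cost is wording in three sections. The contacts are already planned for every participant and the reason for discontinuation is already to be recorded, so no new visit or procedure is added.

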4.13 CONCOMITANT MEDICATIONS

Concomitant use of antiplatelet agents or NSAIDS must be documented in the patient's study record and carefully monitored by the treating physician/site investigator. The use of dual antiplatelet therapy is an exclusion to participation in this study.

4.14 PROPOSED FREQUENCY AND DURATION OF FOLLOW UP

In addition to the initial enrollment visit, patients that are enrolled will receive a telephone follow up at Day-30 +/- 3 days and an in person follow up at Day 90 +/- 3 days.

Post-enrollment follow up visits will include assessment and history for major and minor bleeding, CVC life span, premature CVC removal, CVC lumen occlusion, CVC associated infection and death and assessment of adherence to study drug. Patients will be followed for 90 days +/- 3 days.

4.15 WITHDRAWAL OF SUBJECTS

A subject has completed the study once all follow-up procedures have been completed. Study drug is discontinued, and appropriate clinical management is initiated in the case of the following outcome events (as defined in section 4.5).

For the subjects who reach a study endpoint, subsequent treatment will be left up to the discretion of the treating physician and documented.

If the subject is prematurely discontinued from participation in the study, the study personnel will make every effort to obtain, and record, information about the reasons for discontinuation and any adverse events and if possible perform all safety assessments.

A subject may voluntarily withdraw participation in this study at any time, including for future data collection. If the subject does not return for a scheduled visit, every effort will be made to contact the subject. In any circumstance, every effort will be made to document the reason for withdrawal and when possible, all safety assessments will be done.

All data will be reported for any subject randomized and not completing the study. Subjects withdrawn as a result of an adverse event thought to be related to the study drug will not be replaced. All safety data collected from all subjects during the study will be analyzed.

5 SAFETY

The adverse event reporting period will begin with the first dose of study medication and end on Day-90 +/- 3 days. Adverse events may be collected from participant report or by review of the clinical chart. Adverse events will be documented in the CRF.

Clinical investigators and ultimately the Qualified Investigator (QI) have the primary responsibility for adverse event identification, documentation, grading, assignment of attribution and reporting.

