3.5 WHY IS AN OPEN-LABEL TRIAL DESIGN CHOSEN?

The current standard of care in most cancer patients is to not use outpatient thromboprophylaxis. Patients often receive thromboprophylaxis only when admitted to hospital or subject to additional risks. Not using a placebo tablet reduces study expense and complexity while improving patient acceptance and potentially enrollment into the trial. Since the primary endpoints in the larger planned multicentre study are objective, imaging confirmed thrombosis and bleeding outcomes and not expected to be adversely affected with an open label design.

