5.1 DEFINITIONS

Adverse Events

An Adverse Event (AE) is any untoward medical occurrence in a participant administered at least one dose of study medication; the event does not necessarily have a causal relationship with that treatment or usage. All adverse events (see exception for cancer-related chemotherapy below) will be reported

An adverse event can therefore be:

- All suspected adverse medication reactions.
- All reactions from medication abuse, withdrawal, sensitivity, or toxicity.
- Apparently unrelated illnesses, including the worsening of a pre-existing illness (definition below).
- Injury or accidents.
 - Note that if a medical condition is known to have caused the injury or accident (e.g., a fall secondary to dizziness), the medical condition (dizziness) and the accident (fall) will be reported as two separate AEs.
- Abnormalities in physiological testing or physical examination (findings that require clinical intervention or further investigation beyond ordering a repeat [confirmatory] test).

- Laboratory abnormalities that require clinical intervention or further investigation (beyond ordering a repeat [confirmatory] test) unless they are associated with an already reported clinical event. Laboratory abnormalities associated with a clinical event (e.g., elevated liver enzymes in a subject with jaundice) will be described as a separate AE.

Serious Adverse Events

Serious Adverse Event (SAE)

- An event that results in death
- An event that places the participant at immediate risk of death (a life-threatening event). This does not include an event that, had it occurred in a more severe form, might have caused death.
- Requires participant hospitalization or prolongation of existing hospitalization. For this study, the following exceptions apply to the index hospitalization:
 - Hospitalization for routine administration of chemotherapy/radiation therapy or monitoring of chemotherapy/radiation therapy side effects will not be recorded as a serious adverse event.
- Results in persistent or significant disability/incapacity.
- Is a congenital anomaly/ birth defect
- Other medically important events that, in the opinion of the Site Investigator, may jeopardize the participant or may require intervention to prevent one of the other outcomes listed in the definition above.

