Some conditions may not be immediately life threatening or require hospitalization. Should the investigator feel that the event may jeopardize the participant or may require intervention to prevent more serious outcomes, then it should be treated as serious.

Pre-Existing Conditions

In this trial, a pre-existing condition (i.e., a disorder present before the adverse event reporting period started) should not be reported as an adverse event unless the condition worsens during the adverse event reporting period.

Procedures

Diagnostic and therapeutic non-invasive and invasive procedures, such as surgery, should not be reported as adverse events. However, the medical condition for which the procedure was performed should be reported if it meets the definition of an adverse event.

Laboratory Test Abnormalities

Laboratory test value abnormalities will be reported as an AE if they satisfy one or more of the following conditions for clinical significance:

1. Accompanied by clinical symptoms
2. Leading to a change in study medication (e.g. Dose modification, interruption or permanent discontinuation)
3. Requiring a change in concomitant therapy (e.g. Addition of, interruption of, discontinuation of, or any other change in a concomitant medication, therapy or treatment).

Please note: any laboratory result abnormality fulfilling the criteria for a serious adverse event (SAE) should be reported as such, in addition to being recorded as an adverse event in the CRF.

GRADING OF ADVERSE EVENTS

All adverse events will be graded by the Investigator using the scale below.

1=Mild	Discomfort noticed but no disruption of normal daily activity
2=Moderate	Discomfort sufficient to reduce or affect daily activity
3=Severe	Inability to work or perform normal daily activity

CAUSALITY

Relationship of all adverse events and serious adverse events to the study interventions (causality) should be assessed by the investigator as follows:

- **Unrelated:** There is not a reasonable possibility that the adverse event may have been caused by the study drug.
- **Possibly related:** The adverse event may have been caused by the study drug, however there is insufficient information to determine the likelihood of this possibility.
- **Related:** There is a reasonable possibility that the adverse event may have been caused by the study drug.

EXPECTEDNESS

Adverse events and serious adverse events will also be assessed according to the following categories:

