5.2 RECORDING, REPORTING AND FOLLOW -UP OF ADVERSE EVENTS

Adverse Events Recording

Adverse events will be recorded on the CRF.

The investigator and delegates will record all directly observed adverse events and all adverse events spontaneously reported by the participant. In addition, each participant will be questioned about adverse events at each visit.

Adverse Events Reporting

The QI or delegate will be responsible for reporting the AEs to the OHSNREB, and the Data and Safety Monitoring Board (DSMB) as follows:

- Adverse events will be reported to the OHSNREB as per their guidelines
- Adverse events will be summarized in a table and provided to the Data and Safety Monitoring Board (DSMB) before DSMB meetings.

Serious Adverse Events Reporting

SAEs require prompt or immediate reporting to the QI or delegate. The QI is ultimately responsible for reporting the SAEs to Health Canada, the OHSNREB, the Data and Safety Monitoring Board and Bayer.

Reporting to Health Canada

Serious adverse events that are both unexpected and related or possibly related are subject to expedited reporting to Health Canada. SAEs that are expected or that are unrelated to the study drug are not reportable.

All sites will report to the coordinating centre and the sponsor of the trial will be responsible for reporting the SAE to Health Canada

Report must be filed in the cases:

- I. where the SAE is neither fatal nor life-threatening; within 15 days after becoming aware of the information
- II. where it is fatal or life-threatening, immediately where possible and, in any event, within 7 days after becoming aware of the information

Within 8 days after having informed Health Canada of the SAE, the Qualified investigator will submit as complete as possible, a report which includes an assessment of the importance and implication of any findings.

Each SAE which is subject to expedited reporting should be reported individually using the TRIM-Line form (see Appendix).

Any updated follow up information that becomes available regarding the SAE should be reported in a follow up report.

Reporting to the OHSNREB

All SAEs will be reported to the OHSNREB as per their guidelines.

Reporting to the Data Safety Monitoring Board (DSMB)

SAEs that are related or possibly related and unexpected will be reported immediately to the Chair of the DSMB.

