All SAEs, whether related to the study interventions or not will be summarized in a table, and provided to the DSMB before each scheduled DSMB meeting.

Reporting Procedures for Adverse Events by all sites			
Gravity	Reporting Time	Report to	Type of Report
Serious (fatal or life-threatening) if unexpected and related/possibly related)	Immediately	1) Local REB 2) PI (Ottawa/coordinating Centre) by fax and email	Initial Report
	Within 7 days post initial report then every 15 days if ongoing until end of event		Follow-up/Final Report
Serious (non-fatal or non-life-threatening) whether expected/unexpected or related/unrelated)	Within 24 hours Within 15 days post initial report then every 15 days if ongoing until end of event	1) Local REB 2) PI (Ottawa/coordinating Centre) by fax and email	Initial Report Follow-up/Final Report
AEs	7days	1) PI (Ottawa/coordinating Centre) by entering in	Adverse Event Form in eCRFs

NOTE: In the rare event that the investigator does not become aware of the occurrence of a SAE immediately (e.g., if a trial participant initially seeks treatment elsewhere), the investigator is to report the event within 24 hours after learning of it and document his/her first awareness of the AE.

Adverse Events Follow-Up

Follow-up of adverse events considered related or possibly related to study drugs should continue until they have returned to baseline status or stabilized, or the causal relationship has been changed from related to unrelated to study drug.

Stopping Rules

The study has no formally defined stopping rules. Data will be monitored as they accumulate, and the use of the experimental therapy will cease if there is clear evidence of rivaroxaban-related adverse events or of a lack of efficacy. This decision will be at the discretion of the DSMB

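### Section 5 ties adverse events to a dose of study drug that the observation arm never takes, which contradicts the sections that collect adverse events from everyone

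*Protocol*

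**What the plan says.** Section 5 (Safety) fixes the collection window: "The adverse event reporting period will begin with the first dose of study medication and end on Day-90 +/- 3 days". Section 5.1 fixes the definition: "An Adverse Event (AE) is any untoward medical occurrence in a participant administered at least one dose of study medication". The pre-existing-condition rule in section 5.1 leans on the same window, because it turns on "a disorder present before the adverse event reporting period started".

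The observation arm takes no dose of any kind. Section 4.8 describes it as "No rivaroxaban prophylaxis. Management will be at the discretion of the attending physician". Section 3.5 explains why there is no dummy tablet ("Not using a placebo tablet reduces study expense and complexity"), and the schedule in section 2 limits dispensing to Group 1.

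Other parts of the protocol are written as if AEs come from everyone. Section 5.2 states that "each participant will be questioned about adverse events at each visit". The synopsis gives a 90-day collection period and names neither an arm nor a dose. Section 4.15 commits to analysing the safety data of all subjects.

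The DSMB receives two products of this reporting. For AEs: "Adverse events will be summarized in a table and provided to the Data and Safety Monitoring Board (DSMB) before DSMB meetings". For SAEs: "All SAEs, whether related to the study interventions or not will be summarized in a table", supplied before each scheduled meeting.

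**The concern.** The window and the definition are the rules that sites apply when they decide what to enter. If both depend on a dose, a coordinator following section 5 has nothing to record for an observation-arm participant, while one following section 5.2 or the synopsis would record events in both arms. Either AEs are recorded in one arm only, or recording differs between the three sites.

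A later analysis plan cannot repair this, because events that were never entered cannot be recovered.

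What is at stake is how far the DSMB can interpret its tables. The trial is open-label, section 5.2 sets no formal stopping rule, and ending the experimental therapy for rivaroxaban-related events is left to the board's discretion. Patients with cancer have many intercurrent events. For events other than bleeding, catheter complications and death, the board could lack a concurrent background rate from the same population. It would then lean on the judgement of investigators who know the allocation.

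**Working it through.** The protocol gives no figure to reproduce. The check is a comparison of the text, with one count.

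**Number affected.** Inputs: pilot target of 100 (section 8.2) and 1:1 allocation (section 4.7). Expected observation arm: 100 × 1/2 = 50. If allocation were simple and unrestricted, the 95% binomial range would be 40 to 60. About half is therefore right.

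**Does section 5 reach these participants?**
1. The window opens at the first dose (section 5). With no drug and no placebo (sections 3.5 and 4.8, and the schedule), it never opens.
2. An AE requires at least one dose (section 5.1). With none, no event qualifies.
3. A pre-existing condition is dated from the opening of the window (section 5.1). With no opening, there is no reference date.

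The same wording leaves out events between randomisation and first dose in the rivaroxaban arm, and anyone in that arm who never takes a tablet. An observation-arm participant who crossed over to study drug would be the exception.

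**Does the rest of the protocol agree?**
- Section 5.2, recording: every participant is questioned at every visit. This conflicts with section 5.
- Synopsis: 90 days of collection with no arm limit. This conflicts with section 5, although it names no starting event.
- Section 4.15: safety data from all subjects are analysed. This fits poorly with collection in one arm.
- Schedule: the AE row at Day 30 and Day 90 carries no group label, whereas the dispensing row does. This is weak support, because the compliance row is also unlabelled yet can apply only to people with drug.
- DSMB section (numbered 7.2 in the body): safety review is described in terms of patients exposed to the drug. This points the other way.

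**SAEs.** The seriousness criteria in section 5.1 contain no dose condition, and cancer-related SAEs are to be recorded whatever their cause. On that text alone, control-arm SAEs are collected. They drop out only if the section 5 window, or the AE definition, is taken to govern SAEs as well. The protocol does not settle which.

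**What is not touched.** Section 4.14 assesses bleeding, catheter outcomes (including infection) and death in all enrolled patients. The primary analysis in section 8.1.2 is the recruitment rate. Section 8.1.4 plans no comparison of overall AE or SAE incidence.

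**The case against.** The best case on the other side is that the protocol, read whole, does collect AEs in controls. The synopsis gives an unrestricted 90-day period, section 5.2 questions everyone, and section 10.2 requires a case report form for every randomised subject. A sensible site would use them. This stands as far as it goes. A reader might infer that half the participants have no AE collection anywhere in the protocol, and the synopsis does not support that. The defect is a contradiction between section 5 and these other sections. It is still a defect, because the operative definition and start date are in section 5.

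A second argument is that treated-only collection was a deliberate choice. The DSMB section lends this some support. But section 5 never says so, and section 5.2 would then have staff ask controls about events that have no definition under which to be recorded.

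A third argument is that the stakes are small. Much of this stands. A reader might infer that the trial's safety comparison is lost, or that control-arm SAEs are certainly missing. Neither follows, because bleeding and death are assessed in both arms and the SAE text is ambiguous. Section 5.1 already removes non-serious events possibly related to cancer or its treatment. The board also has expectedness judged against the product monograph, and its own statistician with access to the central database. These help, but expectedness supplies no concurrent control rate, and the database holds only what sites entered. The protocol gives no AE or SAE risks, so the number of control events that would be missed cannot be estimated from it.

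**Conclusion.** The point holds as an internal contradiction about whose adverse events are collected. Under section 5 as written, about 50 of 100 participants have no AE window, no recordable AE and no reference date for pre-existing conditions. The synopsis and sections 4.15 and 5.2 assume otherwise.

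The consequence is confined to the general AE tables that go to the DSMB and, depending on how the SAE text is read, the tables of non-fatal, non-bleeding SAEs. Recruitment, bleeding, catheter outcomes and death are not affected. This conclusion assumes 1:1 allocation of the full target, and that some sites would apply section 5 literally or differently from one another. It should be corrected because the tables inform a discretionary decision in an open-label trial, but it does not threaten the pilot's primary aim.

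**What to change.** In sections 5 and 5.1, define an AE as any untoward medical occurrence in a randomised participant. Start the reporting period at randomisation in both arms and end it at Day 90 (±3 days). Align the synopsis, and date the pre-existing-condition rule from the same point. Section 5.1 currently asks for causality on every AE and SAE, so state there that relation to study drug is assessed only in participants who received it. Tabulate AEs and SAEs by arm for the DSMB.

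If treated-only collection was intended, say so in section 5, state whether it covers SAEs, amend the synopsis and section 5.2 to match, and make no between-arm AE comparison.

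The first option costs wording plus real reporting work for the observation arm. Under the section 5.2 table, AEs are entered within 7 days, and non-fatal SAEs are reported within 24 hours to the local ethics board and the coordinating centre, whether related or not. The visits (section 4.14) and case report forms (section 10.2) are already planned. The second option costs wording only, but gives up the concurrent control counts.
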